7.2.5. Abuse liability

MM-120 is not associated with dependence. Hallucinogens are not self-administered by animals, and there is no human LSD dependence syndrome (Passie et al., 2008). Subjects with current substance use are not included in the study, but substance use disorder in the past is not an exclusion criterion. Hallucinogens have been used and are being investigated in several substance use disorders, including opioid (Belleville et al., 1956; Ross, 2012; Savage et al., 1973), alcohol (Bogenschutz et al., 2015; Krebs et al., 2012; Kurland et al., 1967; Lester, 2014; Ludwig et al., 1969; Mangini, 1998; Pahnke et al., 1970), and nicotine dependence (Johnson et al., 2014).

7.2.6. Neurotoxicity

There is no evidence that the active drug substance of MM-120 (LSD) is neurotoxic (Nichols, 2016; Passie et al., 2014; Passie et al., 2008).

7.2.7. Flashbacks

Flashbacks can be defined as episodic and short (seconds or minutes) replications of elements of previous substance-related experiences (Holland et al., 2011; Passie et al., 2014). These experiences can be positive or negative. Such phenomena have been reported after the use of many substances and are also prevalent in non-substance using persons (Holland et al., 2011). Clinically significant flashbacks are also defined as hallucinogen persisting perception disorder. This disorder is considered rare, but may occur in subjects with anxiety disorders, and it typically will have a limited course of months to a year (Halpern et al., 1999; Holland et al., 2011; Passie et al., 2014). At a follow-up one month after LSD (200 µg) administration, none of 16 healthy subjects reported any perceptual changes (e.g., flashbacks) (Schmid et al., 2018). With regards to the present study, no visual alterations are expected at the doses used, and therefore flashbacks are very unlikely to occur.

7.3 Safety Monitoring

Guidelines for hallucinogen research have been published that relate to high dose (approximately 100 µg and above) use of psychedelics, and not to the low dose (20 µg) used in the present study (Fischman et al., 1998; Gouzoulis-Mayfrank et al., 1998; Johnson et al., 2008). The procedures are intended to support the safe administration of psychoactive substances while minimizing potential adverse reactions. The dose of MM-120 used in the present study is much lower at 20 µg, and safety data is based on previous clinical studies in healthy volunteers.

7.3.1. Other psychiatric disorders

The psychiatric screening criteria are important for minimizing the already low chances of precipitating a longer-term psychotic reaction to MM-120. Subjects who have a present or past history of meeting DSM-5 criteria for schizophrenia, or other psychotic disorders (or due to a medical condition), or bipolar disorder are excluded. The above are the most important conditions to exclude for ensuring safety. Subjects with a first-degree relative with these disorders are also excluded. Other psychiatric disorders such as co-morbid depression, obsessive-compulsive disorders, anxiety or previous substance use disorder are not excluded because hallucinogens have been used in subjects with these disorders, or specifically to treat

these disorders (Gasser, 2012a; Gasser et al., 2015; Grob et al., 2011; Krebs et al., 2012; Moreno et al., 2006; Ross, 2012).

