Exclusion Criteria	
Subjects should not be included in the study if any of the following exclusion criteria are met:
 
1. Past or present diagnosis of a primary psychotic disorder or first degree relative with a psychotic disorder.2. Past or present bipolar disorder (DSM-5).3. Other current psychiatric disorders that, in the opinion of the Investigator or medical supervisor, may confound the results of the study (e.g., obsessive-compulsive disorder, dysthymic disorder, panic disorder, dissociative disorder, anorexia nervosa or bulimia nervosa)4. Subjects with past [REDACTED] to the screening visit) or present history of substance use disorder (except nicotine, provided subject does not smoke more than [REDACTED] cigarettes a day).5. Somatic disorders including Central Nervous System (CNS) involvement of cancer, severe cardiovascular disease, untreated hypertension, severe liver disease (liver enzyme increase by more than 3x the upper limit of normal except unconjugated hyperbilirubinemia due to Gilbert's Disease, per Investigator), severely impaired renal function (estimated creatinine clearance < 50 mL/min by CKD-EPI formula), or anything else that, in the judgment of the Investigator or medical supervisor, poses too great a potential for side effects.6. Any lifetime history of suicide attempt; or [REDACTED] ([REDACTED] active suicidal thoughts or ideation (defined as a suicidal ideation score of 2 or greater in the Columbia-Suicide Severity Rating Scale [C-SSRS]); or endorsement of any suicidal behavior on the C-SSRS within the [REDACTED] to the screening visit.7. Likely to require psychiatric hospitalization during the course of the study.8. Once consent is signed, subject not willing or safely able to stop any prescription or non-prescription ADHD medications during screening and prior to the baseline visit through final study visit, EoS or ET. A list of prohibited medications is provided in Appendix 1.9. Plan to start, stop, or alter the use of any medications, supplements, or other therapeutics from Baseline until the EoS or ET (see Appendix 1 for list of prohibited medications).10. Plan to start, stop or alter the use of psychotherapy, massage, meditation, acupuncture, hypnosis, yoga, or other similar therapy/activity from the time of providing informed consent until EoS or ET.11. [REDACTED] [REDACTED]12. Likely to need any psychiatric medications with the potential to confound interpretation of study results or impact safety, at the discretion of the Investigator, in the 10 weeks following Baseline up to EoS or ET.13. Use of investigational medication/treatment in the past 30 days prior to the screening visit.14. [REDACTED] [REDACTED] at Screening OR Baseline.

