4.2 Exclusion Criteria

Subjects should not be included in the study if any of the following exclusion criteria are met:

1. Past or present diagnosis of a primary psychotic disorder or first-degree relative with a psychotic disorder.
2. Past or present bipolar disorder (DSM-5).
3. Other current psychiatric disorders that, in the opinion of the Investigator or medical supervisor, may confound the results of the study (e.g., obsessive-compulsive disorder, dysthymic disorder, panic disorder, dissociative disorder, anorexia nervosa or bulimia nervosa).
4. Subjects with [REDACTED] substance use disorder (except nicotine, provided subject does not smoke more than [REDACTED] a day).
5. Somatic disorders including Central Nervous System (CNS) involvement of cancer, severe cardiovascular disease, untreated hypertension, severe liver disease (liver

enzyme increase by more than 3x the upper limit of normal except unconjugated hyperbilirubinemia due to Gilbert's Disease, per Investigator), severely impaired renal function (estimated creatinine clearance < 50 mL/min by CKD-EPI formula), or anything else that, in the judgment of the Investigator or medical supervisor, poses too great a potential for side effects.

6. Any lifetime history of suicide attempt; [REDACTED]
[REDACTED] suicidal thoughts or ideation (defined as a suicidal ideation score of 2 or greater in the Columbia-Suicide Severity Rating Scale [C-SSRS]); or endorsement of any suicidal behavior on the C-SSRS within [REDACTED] the screening visit.
7. Likely to require psychiatric hospitalization during the course of the study.
8. Once consent is signed, subject not willing or able to stop any prescription or non-prescription ADHD medications during screening and prior to the baseline visit through final study visit (EoS or ET). *A list of prohibited medications is provided in Appendix 1.*
9. Plan to start, stop, or alter the use of any medications, supplements, or other therapeutics from Baseline until EoS or ET (see Appendix 1 for list of prohibited medications).
10. Plan to start, stop or alter the use of psychotherapy, massage, meditation, acupuncture, hypnosis, yoga, or other similar therapy/activity from the time of providing informed consent until EoS or ET.
11. [REDACTED]
[REDACTED]

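### The safety section says a first-degree relative with bipolar disorder excludes a subject, but no legible eligibility criterion requires it

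*Protocol*

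**What the plan says.** Protocol 7.3.1 (Other psychiatric disorders) presents psychiatric screening as the means of keeping the chance of a longer-term psychotic reaction low. It says that subjects with present or past schizophrenia, "or other psychotic disorders (or due to a medical condition), or bipolar disorder are excluded". It then extends the rule to families: "Subjects with a first-degree relative with these disorders are also excluded".

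The eligibility list words the family rule differently. Criterion 1 of Protocol 4.2 is "Past or present diagnosis of a primary psychotic disorder or first-degree relative with a psychotic disorder". Criterion 2 excludes past or present bipolar disorder and does not mention relatives. The synopsis and SAP 2.1.1 carry the same two criteria with the same scope.

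Protocol 5.1 directs the investigator to Sections 4.1 and 4.2 to determine eligibility before dosing. The opening of Section 4 and Section 5.2 allow no exceptions.

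On two other conditions, 7.3.1 says "Other psychiatric disorders such as co-morbid depression, obsessive-compulsive disorders, anxiety or previous substance use disorder are not excluded", and 7.2.5 says "substance use disorder in the past is not an exclusion criterion". Criterion 3 covers current disorders that the investigator or medical supervisor thinks may confound the results, with the examples "e.g., obsessive-compulsive disorder, dysthymic disorder, panic disorder, dissociative disorder, anorexia nervosa or bulimia nervosa". Criterion 4 in the synopsis covers past substance use disorder, within a period whose length is redacted, "or present history of substance use disorder".

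**The concern.** Section 7 is where an ethics committee or investigator reads how risk is contained. Protocol 7.2.2 accepts that LSD may set off psychotic episodes in people already vulnerable to them, and relies partly on who is enrolled to call this unlikely. If 7.3.1 describes a family-history exclusion that the list does not contain, the written risk mitigation claims more than the eligibility rules require. A candidate whose parent or sibling has bipolar disorder would be described as excluded in one section and would meet no legible exclusion for that reason in the section that decides enrolment.

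**Working it through.** There is no figure to reproduce. The check is a comparison of current text, not of the summary of changes.

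| Source | Excluded in the subject | Excluded through a first-degree relative |
|---|---|---|
| Protocol 7.3.1 | schizophrenia, other psychotic disorders, bipolar disorder | the same disorders, so bipolar disorder is included |
| Protocol 4.2, criteria 1 and 2 | primary psychotic disorder; bipolar disorder | psychotic disorder only |
| Protocol synopsis, criteria 1 and 2 | same as 4.2 | psychotic disorder only |
| SAP 2.1.1, criteria 1 and 2 | same as 4.2 | psychotic disorder only |

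1. **What the family sentence in 7.3.1 refers to.** The disorders just listed are schizophrenia, other psychotic disorders and bipolar disorder. Nothing in the sentence leaves bipolar disorder out.
2. **Whether criterion 1 can be read to include it.** Section 4.2 gives bipolar disorder its own criterion, and 7.3.1 lists it beside the psychotic disorders. The protocol therefore treats it as a separate category, and a clause limited to a psychotic disorder does not plainly reach it.
3. **Which text operates.** Protocol 5.1 points to 4.1 and 4.2, so the narrower rule is the one applied at enrolment.
4. **Whether another criterion supplies it.** Criterion 16 lets the investigator or medical supervisor exclude for any circumstance that may add risk. It does not mention family history and is discretionary, whereas 7.3.1 states a categorical rule. Criterion 11 is wholly redacted and criterion 14 is largely or wholly redacted, so neither can be checked. Criteria 1 and 2 are fully legible.

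The other two conditions compare as follows.

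- **Obsessive-compulsive disorder.** Section 7.3.1 says it is not excluded. Criterion 3 names it as an example, but only if current and judged possibly confounding.
- **Previous substance use disorder.** Sections 7.3.1 and 7.2.5 say it is not excluded. Synopsis criterion 4 excludes it within the redacted period. A disorder that ended before that period may be consistent with all three passages.

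On both, the list is the stricter text.

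**The case against.** The strongest reply is that 7.3.1 is background. Sections 4.1 and 4.2 govern, they agree with the synopsis and the SAP, and an investigator worried about a family history can use criterion 16. It stands that enrolment has one rule. It does not make the statement in 7.3.1 true, and discretion is not the categorical exclusion that 7.3.1 reports.

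A reader might also infer stronger conclusions that the documents do not support:

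- **That the list says the opposite on all three conditions.** It is silent on relatives with bipolar disorder, conditional on obsessive-compulsive disorder, and limited to a redacted period for past substance use disorder.
- **That the bipolar family-history exclusion is never applied.** Criterion 11 cannot be read and criterion 16 permits exclusion case by case. The text supports only that no legible criterion requires it.
- **That the enrolled population would vary with the section a site follows.** Protocol 5.1 and the no-exception rule settle which section applies.
- **That protection is lost on obsessive-compulsive disorder or substance use.** The list is stricter than section 7 on both.
- **That the family data needed are already collected.** SAP 8.3.1 describes one Yes/No item that pools psychiatric and somatic family history, which cannot identify a relative with bipolar disorder.

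**Conclusion.** The point holds for relatives with bipolar disorder. Section 7.3.1 states a safety exclusion that criteria 1 and 2 do not contain, in all three places where they appear, and no legible criterion requires it. This is an internal inconsistency in a rule the protocol presents as a safeguard, and it is wrong as written.

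Its size cannot be put as a count. The documents do not say how often candidates have such a relative, nor how often criterion 16 would be used for one. The conclusion needs no such figure. It rests on the ordinary reading of the family sentence in 7.3.1, on bipolar disorder being a category separate from the psychotic disorders, and on the legible text only.

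The mismatches on obsessive-compulsive disorder and previous substance use disorder are minor alignment matters. Criterion 3 was added in the current protocol version, and the summary of changes lists no edit to 7.3.1, so the older explanation may simply not have been updated. That is an inference.

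**What to change.** Reconcile criterion 1 (Protocol 4.2, synopsis and SAP 2.1.1) with 7.3.1 so that they name the same disorders for first-degree relatives. Either the family clause in criterion 1 takes in bipolar disorder, or 7.3.1 stops claiming it. The sponsor's medical lead decides which; the documents do not settle it. Have section 7 refer to 4.2 rather than restate eligibility.

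In the same amendment, make the statements on obsessive-compulsive disorder and previous substance use disorder in 7.3.1 and 7.2.5 consistent with criteria 3 and 4, again with the direction left to the sponsor. The general statements in 7.3.1 on depression and anxiety should be checked at the same time, because criterion 3 gives dysthymic and panic disorder as examples.

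The cost is a wording amendment and a note to sites. If criterion 1 is widened, add a few more screen failures and a specific question about bipolar disorder in first-degree relatives, because the pooled Yes/No item does not supply that answer. If 7.3.1 is narrowed instead, only text changes. Neither route alters the statistical analysis.

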7.3.2. Predictors for response

Relevant for high-dose psychedelic research, factors that predict more pleasant and mystical-type experiences following hallucinogen administration include high scores of the personality trait of absorption (open to new experiences) and having experienced few psychological problems in the past weeks before the test sessions (Studerus et al., 2012). Factors associated with an unpleasant and/or anxious reaction to the hallucinogen are low age, emotional lability, and a setting involving a brain scan (Johnson et al., 2008; Studerus et al., 2012). With regard to personality, subjects who are more open to new experiences, including the use of hallucinogens, will more likely be interested in participating in the study, and this self-selection bias enhances the safety of such research (Johnson et al., 2008; Studerus et al., 2011).

7.3.3. Drug experience

Previous experience with psychoactive drugs may influence the response to psychoactive substances. In controlled studies with psilocybin, drug use and pre-experience with hallucinogens only moderately affected the psilocybin response (Studerus et al., 2012). Hallucinogen-naïve subjects tended to report overall stronger psilocybin effects (Studerus et al., 2012). Subjects who sometimes smoked cannabis (more than once per month) experienced more pleasurable effects and a trend towards less anxiety compared to subjects who rarely used THC (Studerus et al., 2012). No difference was found in the response to LSD between healthy subjects with previous experience with hallucinogen use and hallucinogen-naïve subjects (Schmid et al., 2015). Of note, subjects with regular drug use were not included in the above study (Studerus et al., 2012). The present study will also include mostly subjects with no or only limited previous drug exposures, similar to previous studies using LSD (Dolder et al., 2017b; Gasser et al., 2014; Gasser et al., 2015; Schmid et al., 2015), and similar to studies conducted by others using psilocybin (Griffiths et al., 2011; Griffiths et al., 2006; Studerus et al., 2011).

7.4 Safety Procedures During the Session

7.4.1. Adverse cardiovascular effects

No clinically relevant cardio-stimulant effects are expected at the dose of MM-120 to be used in the present study. Only mild cardio-stimulant effects are expected at high doses of LSD (Dolder et al., 2016). Cardiovascular effects (blood pressure and heart rate) will be repeatedly measured during the first dosing to document the absence of relevant effects. Closer monitoring would be implemented in the unexpected case of blood pressure values exceeding 180/120 mm Hg or decrease below 90 mm Hg for systolic blood pressure. Treatment of a hypertensive reaction ($P_{sys} > 220$ mmHg) may include lorazepam and nitroglycerine, per Investigator decision and Sponsor medical monitor notified. Treatment of hypotension would include Trendelenburg position. Cardiac arrest would trigger immediate cardiopulmonary reanimation and a call to the ambulance.

7.4.2. Headaches

MM-120 may produce transient headaches (Schmid et al., 2015). One participant (out of 16) required acetaminophen for a moderate headache the day after a LSD session. Conversely, the active drug substance LSD reportedly reduces episodes of cluster headache and migraine (Davenport, 2016; Karst et al., 2010; Sewell et al., 2006), and is currently being tested for these indications in the context of compassionate use, and with authorization of the Swiss Federal Office of Public Health (BAG) in selected cases. In the pilot study with subjects suffering from anxiety associated with life-threatening diseases, LSD markedly reduced the number of migraine attacks in two migraine subjects (Gasser et al., 2014).

7.4.3. AEs between sessions

AE and SAE will be assessed at each study visit and at the follow-up visit at the end of the study.

7.5 Risk Benefit Assessment

7.5.1. Potential benefits

Based on previous anecdotal reports from LSD users practicing repeated low dosing, MM-120 may provide a benefit to ADHD subjects. There is no preliminary data from controlled studies to support a benefit. Therefore, this investigation is the first to explore potential beneficial effects of low doses of LSD in a proof-of-concept study. The study will provide information on the efficacy of MM-120 in the treatment of ADHD, and therefore potentially provide benefit to future subjects, or if efficacy is not supported, help to avoid unnecessary treatment.

7.5.2. Potential harms to subjects

The risk of lasting psychological harm is considered low, and the risks of physical harm very low (see above). The risk of not being provided alternative treatment is minimal and temporary because only subjects who have stopped other treatment options are included or subjects who do not mandatorily need other ADHD medication. The subjects might experience some disadvantage when they stop their medication, which is evaluated as low risk and not life threatening. Subjects are free to stop their study participation at any time without any justification. There are no financial risks. Travel expenses are reimbursed to the subjects.

7.6 Safety Definitions

7.6.1. Adverse Event

An Adverse Event (AE) is any untoward medical occurrence in a clinical trial subject administered an IMP and which does not necessarily have a causal relationship with this treatment. An AE can therefore be any unfavorable and unintended sign (including an abnormal laboratory finding), or any clinically significant change from baseline, whether considered positive (e.g., marked feelings of a drug high, feeling happy) or negative symptom (e.g., feeling panicky, fearful, or sad), change in sleep, quality or duration, or disease temporally associated with the use of an IMP, whether or not considered related to the IMP.

7.6.2. Adverse Reaction

An Adverse Reaction (AR) is any untoward and unintended responses to an IMP judged by Investigator/Sponsor as having a reasonable causal relationship to the IMP. The expression reasonable causal relationship means to convey in general that there is evidence or argument to suggest a causal relationship.

7.6.3. Unexpected Adverse Reaction

An Unexpected Adverse Reaction (UAR) is an adverse reaction (AR), the nature or severity of which is not consistent with the applicable product information (e.g., Investigator's brochure [IB] for an unapproved investigational product or summary of product characteristics [SmPC] for an authorized product). When the outcome of the adverse reaction is not consistent with the applicable product information, this adverse reaction should be considered as unexpected. Side effects documented in the IB, or SmPC which occur in a more severe form than anticipated, are also considered as being unexpected.

7.6.4. Serious Adverse Event or Serious Adverse Reaction

A Serious Adverse Event (SAE) is any untoward medical occurrence or effect that at any dose results in death, is life-threatening, requires hospitalization, or prolongation of existing hospitalization, results in persistent or significant disability, or incapacity, or is a congenital anomaly or birth defect. In this context, the term life-threatening refers to an event in which the trial participant was at immediate risk of death at the time of the event; it does not refer to an event which might have caused death if it were more severe.

A Serious Adverse Reaction (SAR) is an SAE that is determined to be related to the intervention. Based on the causality definitions in Section 10.7, SAEs that are determined to have a causal relationship of "possible", "probable" or "definitely" will be considered SARs.

